### Analysis of primary objective:

Standard life table methods will be used to analyze PFS. We will report the 4-month, 1-year and median PFS with 95% confidence intervals for both arms of the study.

### Analysis of secondary objectives:

1. The 4-month PFS will be compared between arms of the study using a one-sided, 0.05 alpha level, log-rank test.
2. All patients included in the study must be assessed for response to treatment, even if there are major protocol treatment deviations. Each patient will be assigned one of the following categories: 1) complete response, 2) partial response, 3) stable disease, 4) progressive disease, 5) early death from malignant disease, 6) early death from toxicity, 7) early death because of other cause, or 9) unknown (not assessable, insufficient data).  
All subjects in the study will be included in the main analysis of the response rate. Patients in response categories 4-9 should be considered to have a treatment failure (disease progression). Thus, an incorrect treatment schedule or drug administration does not result in exclusion from the analysis of the response rate. Response rate will be estimated overall and by treatment arm. A Fisher's Exact or chi square test will be use to compare response rates across treatment arms.
3. Standard life table methods will be used to analyze OS. Four month, 1-year and median survival will be reported, overall and by treatment arm. We acknowledge that OS assessment will be compromised with the cross-over design and will report as such.
4. Baseline global methylation will be categorized as high or low and OS Kaplan Meier curves plotted by category. The change in global methylation will be categorized as positive or negative and OS Kaplan Meier curves plotted by category. Similar analyses will be used for individual expression markers.
5. Pharmacokinetic (PK) sampling studies are proposed for all participating patients who undergo pharmacodynamic endpoints. Single dose PK samples will be collected on Cycle1, Day 1, at the following time points: pre-dose 0.25, 0.5, 1, 1.5, 2, 3, 4, 6, and 8 hr. The following PK parameters describing the concentration time profile of SGI-110 and Irinotecan will be calculated: total exposure will be calculated as area under the plasma concentration-time curve (AUC) using the linear trapezoidal rule by using noncompartmental methods (Winonlin, version 5.3) and/or compartmental modeling (Adapt II, release 4.0). Other parameters such as maximum concentration ( $C_{max}$ ), time to maximal concentration ( $T_{max}$ ) and half-life ( $T_{1/2}$ ) will also be calculated.  $C_{max}$  and  $T_{max}$  will be obtained from the data, while the half-life will be calculated as  $0.693/k$ , where  $k$  is the slope of terminal elimination phase. Associations between SGI-110 exposure parameters

CONFIDENTIAL

This document is confidential. Do not disclose or use except as authorized.

(Cmax and AUC) and pharmacodynamic endpoints (i.e., global methylation changes toxicity and toxicity) will be assessed using appropriate non-parametric statistical tests.

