#### Phase II Component: Stage II

- To evaluate response rate as determined by RECIST criteria 1.1
- To evaluate concurrent SGI-110+irinotecan treatment versus regorafenib or TAS-102 alone
- To improve median overall survival from historical rate of 6.4 months
- To assess for potential predictive biomarkers of response and survival using baseline tissue

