**Phase II secondary objectives:**

1. Evaluate and compare response rates between arms of the study as determined by RECIST criteria 1.1.
2. Evaluate and compare overall survival (OS) between arms of the study.
3. Assess for potential predictive markers of survival using baseline tissue.
4. To assess the pharmacokinetics of SGI-110 in metastatic colon cancer patients and correlate with changes in global methylation.

**Sample Size/Accrual Rate:** The median PFS of patients on the phase III CORRECT trial of Regorafenib in metastatic colorectal cancer reported by Grothey and Van Cutsem was 1.9 months. The median PFS of patients on the phase III RECURSE trial of TAS-102 in metastatic colorectal adenocarcinoma reported by Mayer was 2.0 months. The PFS curves of these two trials were superimposable and therefore hazard rates over four time intervals were estimated based on the published PFS curve (figure 3.) for Regorafenib from the CORRECT trial. Simple linear regressions were used to fit the natural logarithm of the Kaplan-Meier product limit estimate of the PFS function as a function of time in four intervals: from 1 to 6 weeks, 6 to 12, 12 to 18, and 18 to 56 weeks. These estimated hazard rates: 0.0113, 0.0558, 0.3238, and 0.0748 per person week were used in simulations to evaluate power for this study. We hypothesize that the SGI-110 combination treatment will improve the 4 month PFS from 23% to 46.5%. Patients will be randomized to the SGI-110 + irinotecan (Arm A) and the Regorafenib or TAS-102 arm (Arm B) in a 2:1 ratio. Using a one sided 5% type I error allowance, accrual of 48 patients per year for 2 years (Arm A and B target sample sizes of 64 and 32 respectively) with an additional 2 years of follow up, this study will provide sufficient events to have 83% power to detect an improvement of the median PFS from 1.9 months to 3.6 months, i.e. a hazard ratio of 0.526.

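### The predictive-marker objective is analysed by OS curves per marker category with no arm or arm-by-marker contrast, which cannot separate a predictive from a prognostic marker

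*Combined protocol and SAP*

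**What the plan says.** The objective appears twice. Section 1.3 (Phase II Component) gives it as "To assess for potential predictive biomarkers of response and survival using baseline tissue". Section 14.1 (Phase II secondary objectives) gives it as "Assess for potential predictive markers of survival using baseline tissue".

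The analysis is item 4 under Analysis of secondary objectives in section 14.1. For the baseline marker: "Baseline global methylation will be categorized as high or low and OS Kaplan Meier curves plotted by category". For the post-treatment change: "The change in global methylation will be categorized as positive or negative and OS Kaplan Meier curves plotted by category". For the rest: "Similar analyses will be used for individual expression markers". Item 4 gives no arm, model, interaction, test or cut-point.

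The neighbouring items do name the arm. Item 2 says "Response rate will be estimated overall and by treatment arm" and item 3 says "Four month, 1-year and median survival will be reported, overall and by treatment arm". Item 3 also says of the endpoint that item 4 uses: "We acknowledge that OS assessment will be compromised with the cross-over design".

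On tissue, the phase II research biopsies come from 36 Arm A patients only (sections 5.2.1 and 8.3.1). Archival tissue is to be procured if available (section 3.1.4), is on the calendars of Arm A and both Arm B regimens (section 9), and is already intended for methylation analysis (section 8.1).

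**The concern.** A marker predicts benefit from SGI-110 plus irinotecan only if the treatment effect differs between marker levels. That is a contrast of contrasts: arm A versus arm B among marker-high patients, against the same comparison among marker-low patients. Curves by marker category alone show only whether the marker goes with survival, which any prognostic factor also does.

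The randomised control arm that could answer the question exists, but item 4 does not use it. At stake is the reading of a secondary result. A marker that merely tracks good prognosis could be taken forward as a selection marker for this combination.

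**Working it through.** The documents give no sample size, effect size or power for the marker objective, so there is no stated figure to reproduce.

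**1. Can the planned curves separate the two kinds of marker?**

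Inputs from the documents: 2:1 allocation (64 and 32), a historical median OS of 6.4 months (section 1.3), and a hazard ratio of 0.526, borrowed from the PFS design only as a plausible size. Assumed: exponential OS, 50% marker prevalence, no crossover effect. The medians and hazard ratios come from a large-sample simulation.

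| | Purely predictive: HR 0.526 for marker-positive in Arm A, no marker effect in Arm B | Purely prognostic: same HR (0.64 to 0.66) in both arms, no treatment effect |
|---|---|---|
| Pooled medians, negative vs positive | 6.4 vs 9.7 months | 6.4 vs 9.7 to 10.0 months |
| Pooled marker HR | 0.64 | 0.64 to 0.67 |
| Marker HR in Arm A | 0.53 | about 0.65 |
| Marker HR in Arm B | 0.99 | about 0.65 |

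Hand check of the medians. In the prognostic case with HR 0.66, 6.4/0.66 = 9.7 months. In the predictive case, the marker-positive pool is two thirds Arm A and one third Arm B. With λ = ln 2/6.4 = 0.1083, survival at 9.7 months is (2/3)·exp(−0.526·0.1083·9.7) + (1/3)·exp(−0.1083·9.7) ≈ 0.38 + 0.12 = 0.50.

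Pooled, the two cases look the same. By arm, they separate.

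Using Arm A alone does not help. A marker that is prognostic with HR 0.526 in both arms gives Arm A medians of about 6.4 and 12.1 months, as does the purely predictive marker (6.4/0.526 ≈ 12.2).

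**2. How readily would a purely prognostic marker separate the curves?**

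Item 4 contains no test, so one is added for illustration: two-sided 5% log-rank, 50% prevalence, every patient with a marker result and an event. All of this is assumed. Approximate power = Φ(|ln HR|·√d/2 − 1.96), with d = 96 (all patients) or 36 (biopsy subset).

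| Prognostic HR | d = 96 | d = 36 |
|---|---|---|
| 0.5 | Φ(3.40 − 1.96) = 92%; simulated 91% | Φ(2.08 − 1.96) = 55%; simulated 49% |
| 0.7 | Φ(1.75 − 1.96) = 42% | Φ(1.07 − 1.96) = 19% |
| 0.8 | Φ(1.09 − 1.96) = 19% | Φ(0.67 − 1.96) = 10% |

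At HR 0.5 the simulated figures (3,000 trials) are used in the text, because the approximation is optimistic there.

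**3. What would an arm-by-marker contrast deliver?**

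SE of the log ratio of hazard ratios = √(Σ 1/events) over the four arm-by-marker cells.

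- Best case, 96 events with complete tissue: cells of 32, 32, 16 and 16. SE = √(2/32 + 2/16) = √0.1875 = 0.433. The 95% interval around a ratio of 1 is exp(±1.96·0.433) = 0.43 to 2.34.
- Half the tissue, 48 events: cells of 16, 16, 8 and 8. SE = √0.375 = 0.612. The interval is exp(±1.96·0.612) = 0.30 to 3.32.
- Two-sided 5% power for a true ratio of 0.526 (|ln| = 0.642): Φ(0.642/0.433 − 1.96) = 32% at best, and Φ(0.642/0.612 − 1.96) = 18% with half the tissue.

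**The case against.** The strongest defence is that item 4 is descriptive and exploratory. It plots curves, tests nothing, and supports no decision on alpha, sample size or patient selection. The objective says potential, and predictive markers of survival can be read loosely as markers that forecast outcome. The trial could not power an interaction, and nobody knows how many archival blocks will arrive: section 3.1.4 asks for them only if available, and section 8.1 wants them chiefly to compare primary with metastatic lesions.

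Much of this stands. It limits the severity and rules out a confirmatory remedy. It does not make the curves informative about prediction. Low power argues for reporting a wide interval, not for leaving out the contrast that defines the objective.

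Four stronger readings are tempting, and the documents do not support them:

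- That the plan pools the arms. Item 4 is silent on arm. The point holds because the pooled and the Arm-A-only readings both fail.
- That 91% or 49% is a false-positive rate of the plan. These figures are the power of an added test under one assumed hazard ratio, and they fall steeply as that ratio nears 1.
- That Arm-A-only results could safely be labelled prognostic. A purely predictive marker separates the Arm A curves just as well, so that label is equally unsupported.
- That crossover spoils every item 4 curve. It runs only from Arm B to Arm A (section 5.8), so it does not touch curves limited to Arm A biopsies. It does blur a between-arm OS contrast.

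**Conclusion.** The point holds as a mismatch between objective and analysis, and no stated number is overturned. Sections 1.3 and 14.1 ask about predictive markers. The one planned phase II marker-outcome analysis cannot distinguish prediction from prognosis under either reading of which patients it includes. That conclusion is logical and needs no assumed effect size.

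The illustrative frequencies run from about 91% (n=96) or 49% (n=36) at HR 0.5, through 42% or 19% at 0.7, to 19% or 10% at 0.8. They rest on 50% prevalence, complete marker and event data, and an added test, none of which is in the documents. Nothing in the plan says that a separating marker will be declared predictive, so the harm is a risk of misreading and not a planned false claim.

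The change should be made: it needs no new samples and little effort. The objective is secondary, and the result can only be an exploratory estimate.

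**What to change.** In item 4:

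- For the baseline marker measured on archival tissue in both arms, where available, show PFS and OS by marker category within each arm. PFS is the primary endpoint and is less exposed to crossover.
- Fit a Cox model with arm, marker and an arm-by-marker term. Report the interaction ratio with its 95% interval, labelled exploratory, and the number of patients with tissue in each arm.
- Describe results from Arm A biopsies only, including change in methylation, as associations within Arm A that cannot distinguish predictive from prognostic.
- If Arm B tissue proves too sparse, reword the objective in sections 1.3 and 14.1 as association with outcome.

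The cost is a little extra analysis. The downside is the low precision shown above, made worse by however much archival tissue is missing.

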**Figure 1: LINE demethylation**

There have been 5 documented major responses (2 CRs and 2 CRi, 1 CRp) all in heavily-pretreated refractory AML subjects regardless of prior hypomethylating agents (HMA) treatment : 1 CR and CRp with weekly (60 mg/m^2 and 125mg/m^2, respectively) and 2 CRi and 1 CR with daily (36/60 mg/m^2 and 60 mg/m^2 respectively). The major responses were observed in 5/19 refractory AML patients when adequate hypomethylation (>10%) was achieved. Five MDS patients who all received prior treatment with HMAs had hematological improvements or marrow CR.

As of 27 March 2012, there were 54 subjects who have information in the clinical database in the Phase 1/2 study with single-agent SGI-110. This data cutoff date includes all subjects in both cohorts up to Cohort 5.

Of the 54 subjects in the clinical database, 46 (85%) have reported at least 1 adverse event (AE). There were 26 (48%) subjects with an AE considered related by the Investigator. The most common related AEs, occurring in at least 3 subjects (6%) in decreasing incidence were injection site pain (n=12, 22%); fatigue (n=6, 11%); nausea (n=5, 9%); and thrombocytopenia, anaemia and diarrhea (n=3, 6%). All of these were Grade 1 or 2 AEs with the exception of 1 subject (1 in 60 mg/m^2 dailyx5) with Grade 4 thrombocytopenia and 2 subjects (1 in 3 mg/m^2 dailyx5 and 1 in 60 mg/m^2 dailyx5) with Grade 3 anaemia.

As of 31 May 2012, there were 156 serious adverse events (SAEs) in 66 subjects in the safety database regardless of relationship to the study drug. The most common SAEs (≥5%) were febrile neutropenia (n=24, 36%), pneumonia (n=17, 26%), disease progression (n=7, 11%), sepsis (n=6, 8%), pyrexia (n=5, 9%), bacteraemia and skin infection (n=4, 6% each). Most events were considered not related to study drug as they were expected from disease progression of the study population (MDS and AML). Twelve (12) subjects had SAEs considered by the investigator as related to the use of SGI-110: 3 subjects with febrile neutropenia, 2 subjects with thrombocytopenia, and 1 subject each with pseudomonal sepsis, atrial fibrillation, chest pain, pleural effusion, bacteraemia, sepsis and dysphagia.

CONFIDENTIAL

This document is confidential. Do not disclose or use except as authorized.

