**8.3 Pharmacodynamic Studies**

8.3.1 Tumor Biopsies

Mandatory tumor biopsies will be required at baseline and on Cycle 1 Day 8 in the phase I cohort. Tumor biopsies at baseline and during Cycle 2 (between C2D8 and C2D15) will also be collected from the first 36 patients enrolled in the phase II cohort with biopsiable disease randomized to SGI-110 + Irinotecan (Arm A) approximately evenly spread between the following study sites: SKCCC, VUMC, MSKCCC, and USC-Norris. Core biopsies are required; 4-6 passes must be obtained. Fine needle aspiration biopsies may be allowed only after PI approval. Pre- and post- biopsy should be performed from same organ site. For example: if

pre- biopsy is liver, then post- biopsy should also be liver and preferably the same lesion. Biopsy sites (liver, colon, intra-abdominal implants) in metastatic colorectal cancer are generally amenable to biopsy, and pre- and post-treatment tissue sampling is an important strength of this study. Post-treatment biopsies will be done ~cycle 1 day 8 (and between C2D8 and C2D15 during the phase II portion of the study). The timing of the post-treatment biopsy will be performed based on prior experience in the leukemic patients where the majority of demethylation events have been seen at between 8-15 days of each cycle. Patients with baseline biopsies who remain on the trial beyond 6 cycles will be asked to participate in another research biopsy between cycles 6-9.

There was no comparable data in solid tumors. All biopsy specimens will be stored as fresh tissue at least -70°C for extraction of DNA and RNA. Biopsy specimens will be studied for tumor methylation profiles, as described below. Evaluation of expression of genes that become demethylated post-treatment will be performed using quantitative real-time PCR and/or expression arrays. If an attempt at biopsy is unsuccessful, the patient will still be eligible for treatment and the subsequent biopsies will be foregone. Tumor biopsies and plasma from the phase I portion of the trial will be analyzed prior to moving onto phase II for demethylation and the timing of the biopsies in the phase II component of the trial may be adjusted based on these results. As of December 2015, our Phase I data showed no clear pattern in demethylation at C1D8, while serum demethylation appeared to have a delayed and dose-dependent nadir in the middle of cycle 2, therefore timing of the second biopsy was moved to C2D8-15.

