	
a: Arm A -Dose Level 1G from Phase I, SGI-110 45mg/m2 D1-5, Irinotecan 125mg/m2 D8 and 15. Treatment cycle is 28 days. Growth factor support of filgrastim (or institutional equivalent) 5mcg/kg/day on days 9-14 and peg-filgrastim 6mg on day 16 of cycle 1 is mandatory. Additional growth factor support during Cycle 1 and on subsequent cycles will be provided per clinician judgment.
 
b: All study calendar evaluations for cycle 3 are representative of cycle 3 and beyond.
 
c: Off-study evaluation should be performed within 30 days of last dose.
 
d: Albumin, alkaline phosphatase, total bilirubin, BUN, calcium, chloride, glucose, phosphorus, potassium, total protein, SGOT [AST], SGPT [ALT], sodium.
 
f: Serum pregnancy test (women of childbearing potential). g: Baseline height will be measured and recorded once pre-study, and this value for height will be used through the patient's duration of study
 
h: SKCCC, VUMC, MSKCCC, and USC-Norris, will obtain biopsies on a total of 36 patients (distributed roughly evenly between the sites) for the first patients enrolled to the phase 2 if they have both biopsiable disease and are randomized to SGI-110 + Irinotecan. Additional optional biopsy will be requested of patients with baseline research biopsy who remain on trial through Cycle 6-9.
 
i: QoL surveys will be done on C3D1 and every other cycle subsequently (i.e. Cycle 5 Day 1, Cycle 7 Day 1, etc)

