**Moving to Phase II Component:** Our hypothesis is that SGI-110 treatment will sensitize colon cancer patients to retreatment with irinotecan. Accordingly, it will be important to see that the dose of SGI-110 that is at the MTD does have pharmacodynamics effects at the tumor level. Patient tumor biopsies post-treatment will be analyzed by LINE assay for demethylation to assess for at least 10% demethylation from baseline in the tumor biopsies. We aim to see this level of demethylation in at least 60% of post-treatment biopsies as previously described in phase O studies.

**Phase II primary objective:** Evaluate the progression free survival (PFS) in patients receiving combination SGI-110 plus Irinotecan compared to standard of care treatment with regorafenib or TAS-102. Events are defined as disease progression or death from any cause. All patients treated

CONFIDENTIAL

This document is confidential. Do not disclose or use except as authorized.

on protocol will be included in the determination of PFS, regardless of treatment modification or discontinuation.

Epigenetic therapy may take several cycles to exert its maximal benefit, and preclinical data has demonstrated initial tumor growth is possible prior to tumor shrinkage. Patients on treatment with SGI-110 and IRI will be allowed to remain on study if their tumor progresses on RECIST 1.1 criteria if they are 1) clinically stable, 2) their provider feels it would be in their best interest, and 3) the patient is informed of scan results and consents to remain on treatment. In this circumstance, they will be reimaged on schedule after 2 further cycles. If this subsequent imaging confirms progressive disease, the date of the progression even will be dated to the first (initial) scan date that progression was first documented.

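### Change in tumour methylation, read as its sign, and baseline methylation as high or low, are reduced to two-group OS plots; a continuous exploratory Cox model would use the same biopsies better

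*Combined protocol and SAP*

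**What the plan says.** Section 14.1, Analysis of secondary objectives, item 4, sets out the link between methylation and survival: "The change in global methylation will be categorized as positive or negative and OS Kaplan Meier curves plotted by category". Baseline global methylation is handled the same way, as high or low, and individual expression markers follow the same pattern. The item gives no definition of any category, no model or test, no patient set, and does not say whether change is measured in tissue or plasma. No time origin for OS is stated.

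Elsewhere the plan has a yardstick for demethylation. The Moving to Phase II Component paragraph of Section 14.1 uses the LINE assay "to assess for at least 10% demethylation from baseline in the tumor biopsies" and adds: "We aim to see this level of demethylation in at least 60% of post-treatment biopsies". In Section 2.1.6, the background responses in AML are reported for patients "when adequate hypomethylation (>10%) was achieved". Item 4 does not refer to this criterion.

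The phase II pairs come from Section 8.3.1: "Tumor biopsies at baseline and during Cycle 2 (between C2D8 and C2D15) will also be collected from the first 36 patients enrolled", limited to Arm A patients with biopsiable disease. Section 8.3.1 also allows for unsuccessful biopsy attempts, so 36 pairs is a ceiling.

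**The concern.** Change in methylation is a continuous measurement. Splitting it by sign puts a very small fall, which may be assay noise, in the same group as a large one. If the drug does what the plan hopes, few patients will be in the positive group and that curve will rest on a handful of people. If the drug does not demethylate, the two groups are made by chance. Up to 36 patients are asked for two research biopsies to test the mechanism. The planned plot would give no effect estimate and would use only part of what the pairs contain.

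**Working it through.** The documents give no sample size, event count or power for this analysis, so there is no planned figure to reproduce.

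**Inputs from the documents.** At most 36 pairs (Section 8.3.1). Target of at least 10% demethylation in 60% of biopsies (Section 14.1). Second biopsy at C2D8 to C2D15 with 28-day cycles, that is 28 + 7 = 35 to 28 + 14 = 42 days after C1D1. Historical median OS of 6.4 months (Section 1.3).

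**Assumptions.** Change is normally distributed. Its SD is not in the documents, so 5 to 30 percentage points is shown.

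**1. Group sizes if the target is just met.** P(change ≤ −10) = 0.60 requires mean = −10 − 0.2533 × SD. At SD 10 the mean is −12.53, and P(change > 0) = 1 − Φ(1.253) = 0.105, so 36 × 0.105 = 3.8 pairs are positive.

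**2. Information kept.** For a roughly linear effect, a two-group split keeps φ(z)²/[p(1 − p)] of the information in a normal covariate, where z is the standardised cut and p the share below it. At the 10% cut z = 0.2533 and p = 0.60, which gives 0.62 at every SD.

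| SD | Positive, of 36 | Fall of less than 10%, pooled with larger falls | Information kept, zero cut | Information kept, 10% cut |
|---|---|---|---|---|
| 5 | 0.4 | 14.0 | 8% | 62% |
| 8 | 2.4 | 12.0 | 27% | 62% |
| 10 | 3.8 | 10.6 | 35% | 62% |
| 12 | 5.0 | 9.4 | 41% | 62% |
| 20 | 8.1 | 6.3 | 52% | 62% |
| 30 | 10.0 | 4.4 | 56% | 62% |

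**3. If the target is not met.** At mean change 0 the sign split is 18:18 and keeps 64%. The 10% cut then keeps 35% to 49% (SD 8 to 12), with about 4 to 7 patients beyond it. At mean −5 the two cuts keep equal amounts. No fixed cut is best throughout; under a linear effect the continuous covariate keeps 100% by definition.

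**4. Simulation, effect located at the 10% threshold.** 36 patients, exponential OS with median 6.4 months in those below the threshold, HR 0.5 above it, two-sided 5% log-rank test. Rejection is 20% (SD 10) or 28% (SD 20) with the zero cut, and 45% or 47% with the 10% cut.

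**5. Ceiling on precision.** Schoenfeld's formula at HR 0.5, two-sided 5%: power = Φ(|ln 0.5| × √(d × a × (1 − a)) − 1.96), with d deaths and a the share in one group. With d = 36 and a = 0.60, power = Φ(0.693 × √8.64 − 1.96) = Φ(0.077) = 53%. With 31 deaths it is 47%, and with 25 it is 40%. Power of 80% needs 69 deaths, more than 36 pairs can supply.

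**6. Timing.** Every classified patient has survived to the second biopsy, 35 to 42 days (about 1.15 to 1.4 months). At a 6.4-month median, 31 to 32 of 36 would be alive then. In the simulation, log-rank z values timed from treatment start and from the second biopsy correlate at 0.999, and at SD 10 both reject in 45% at HR 0.5 with the 10% cut.

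**The case against.** The strongest case against is that this is a descriptive plot with no test, on a question the objectives barely raise: the phase II objective on predictive markers names baseline tissue only. The paired biopsies are also used elsewhere (Section 8.3.1.1 compares pre- and post-treatment methylation and relates it to expression). Positive and negative are undefined, so a split at zero is an inference. All of this is fair, and it limits the point to an inexpensive improvement. It does not remove it: if the terms mean something other than the sign, the plan does not say what.

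The size of the loss depends on unstated inputs. At SD 20 to 30 the zero and 10% cuts keep nearly the same information. Section 8.3.1 reports no clear demethylation pattern at C1D8 in phase I, so the 60% target may not be met at the later biopsy either. This stands, and it argues against choosing any one cut for the analysis.

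A reader might also infer three stronger claims.

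- **That the 10% criterion is the right outcome cut.** The documents use it as a condition for moving to phase II and as AML background, where responses above 10% are given with no rate below it. Near a zero mean change it keeps less information than the sign.
- **That the missing landmark biases the curves.** Both categories require a second biopsy in the same one-week window, so the guaranteed survival is common to both. The plan nowhere puts patients without a second biopsy in a category.
- **That these choices make the biopsies uninformative.** The number of pairs is the main limit.

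**Conclusion.** The point holds as an improvement to an exploratory analysis. Read as the sign of the change, item 4 leaves about 0 to 10 of 36 pairs in the positive group if the 60% target is just met (2 to 5 at SD 8 to 12), and pools 4 to 14 patients with under 10% demethylation with those above it. It keeps 8% to 56% of the linear information across SD 5 to 30 (27% to 41% at SD 8 to 12). With no mean change the split is about 18:18 by noise. These figures rest on normal changes, an assumed SD, all 36 pairs being obtained and a roughly linear effect on the log hazard.

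The continuous analysis is preferable whether or not the target is met, because it does not depend on where the changes centre. Timing OS from the second biopsy would tidy the absolute survival estimates but would not materially alter the comparison. Neither change makes the analysis confirmatory.

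**What to change.** Replace the categorisation in item 4 with the following:

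- Analyse change in LINE-1 methylation, and baseline methylation, as continuous covariates in an exploratory Cox model for OS, and report the hazard ratio with its 95% confidence interval.
- Restrict the change analysis to patients with both biopsies, and name the specimen.
- Keep Kaplan-Meier curves for display only, with cut-points fixed in advance: for example the plan's 10% criterion for change and the median for baseline.
- State the OS time origin; for the change analysis, the second biopsy date is the tidier choice.
- Label the results hypothesis-generating.

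The cost is a change of SAP wording and one extra exploratory model on the same samples and assays. The model assumes an approximately log-linear effect, which at most 36 pairs can check only weakly, and the confidence interval will be wide.
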